7. TREATMENT OF SUBJECTS

Psychological First Aid (PFA)

All participants, both in the treatment and the comparison group, will be offered individual Psychological First Aid (PFA) through a face-to-face or teleconferencing meeting. PFA is a WHO developed support strategy that involves humane, supportive and practical help for individuals suffering from serious humanitarian crises. PFA does not necessarily involve a discussion of the event(s) that cause the distress but aims particularly at five basic elements that are crucial to promote in the aftermath of crises, i.e. a sense of safety, calm, self- and community efficacy, connectedness, and hope (Hobfoll et al., 2007). PFA consists of a (telephone) conversation (approximately 30-45 minutes) that a helper has with a participant. PFA has various themes; in PFA, the helper provides non-intruding practical care and support, assesses needs and concerns, helps people to address basic needs (e.g. information), listens to people without pressuring them to talk, comforts people and helps them to feel calm, helps people to connect to information, services, and social support, and protects people from further harm (WHO, 2011).

Care-as-usual (CAU)

In addition to PFA, both the treatment and the comparison group will receive care-as-usual (CAU); they will be allowed to receive any usual care. CAU may include community care, social/legal support, and psychoeducation. Because ARM may have a lack of knowledge of the Italian health care system and therefore may not utilize health care (Aanjaagteam Bescherming Arbeidsmigranten, 2020), we will inform them on the Italian health care system as well. Additionally, participants will receive information about locally available referral options. We will record for all participants whether they have a general practitioner (when they consent to having this recorded). In case the participant gives approval, we will record name and contact details.

7.1. INVESTIGATIONAL PRODUCT/TREATMENT

Treatment group: Stepped-care Doing What Matters/Problem Management Plus (DWM/PM+)

Stepped-care models assume to provide health care in the most efficient and cost-effective way: the first step of care is readily available for all those in need and more costly treatments are reserved only for those not improving. Evidence suggest that stepped-care models are modestly effective (van Straten, Hill, Richards & Cuijpers, 2014; Ho, Yeung, Ng & Chan, 2016) although there is a high heterogeneity of such models (number of steps, duration of steps, rules about stepping up) and their effects. Interestingly, research in clinical practice has shown that results improve when care providers switch from a matched care to a stepped-care approach (Boyd, Baker & Reilly, 2019). The treatment group will receive the stepped-care program consisting of Doing What Matters in Times of Stress (DWM) (step 1) and Problem Management Plus (PM+) (step 2) in addition to Psychological First Aid (PFA) and care-as-usual (CAU) (for details of CAU, see: 'Care-as-usual (CAU)' below). Step 2 will only be provided if the participant still has elevated levels of psychological distress ($K10 > 15.9$) at 2 weeks after DWM, i.e. during the second quantitative assessment.

Step 1: Doing What Matters in Times of Stress (DWM)

The DWM program has been developed by WHO and collaborators working in the humanitarian field. DWM was designed to be relevant for large segments of adversity-affected populations: it is intended to be transdiagnostic, easily adaptable to different cultures and languages, and both meaningful and safe for people with and without mental disorders. DWM is based on acceptance and commitment therapy (ACT), a form of cognitive-behavioral therapy, with

distinct features (Hayes, Levin, Plumb-Villardaga, Villatte & Pistorello, 2013). ACT is based on the concept that ongoing attempts to suppress unwanted thoughts and feelings can make these problems worse, so instead it emphasizes on learning new ways to accommodate these thoughts and feelings without letting them dominate. ACT has been shown to be useful for a range of mental health issues (Tjak et al., 2015) and has been used successfully in a guided self-help format (Hayes et al., 2013).

The DWM program consists of a self-help guide that is complemented with pre-recorded audio exercises. The audio material imparts key information about stress management and guides participants through individual exercises. Additionally, participants are guided by a briefly trained helper.

DWM includes five sections (or modules), each of which focuses on a specific skill:

- **Section 1: *Grounding*:** Bringing attention back to the present moment when caught up in distressing emotions.
- **Section 2: *Unhooking*:** Noticing difficult thoughts and feelings, naming difficult thoughts and feelings, and refocusing on what you are doing.
- **Section 3: *Acting on your values*:** Identifying personal values and then taking small or big actions to live in line with these values.
- **Section 4: *Being kind*:** Enhancing and encouraging kindness towards oneself and towards others.
- **Section 5: *Making room*:** Learning how to tolerate stress while still acting consistently with values.

In this study, the DWM program will be delivered as an online intervention. The DWM intervention, i.e. both the audios and the self-help guide, have been adapted for use on a smartphone or other device with internet access. The format of DWM is innovative in that it seeks to ensure that key intervention components are delivered as intended through the use of pre-recorded audio, without the burden of extensive training and supervision. In the online application tool a new module (i.e. section) is released every week so participants will be asked to go through the entire DWM intervention within five weeks with weekly guidance from a helper. Due to its format, the DWM program does not require much time from experts for implementation. The delivery mode for the support from the helper will be flexible and in line with COVID-19 regulations. The potential of using a psycho-educational course to access hard-to-reach populations has been demonstrated previously (Cuijpers, Munoz, Clarke & Lewinsohn, 2009). Additionally, research has found that guided self-help programs produce much better results than “pure” (unguided) self-help, and the effects produced by guided self-help are surprisingly similar to face-to-face psychological treatment (Fledderus, Bohlmeijer, Pieterse & Schreurs, 2012).

Protocol adherence

We will assess DWM protocol adherence at post-intervention based on meta-data collected during the intervention (i.e. by tracking participants usage of the DWM app such as who accesses what page, how often, how much time participants spend on the app etc.). We will only use this meta-data during the intervention to remind each participant (e.g. through e-mail) after finishing each module to let them know that they should start a new module. Additionally, participants receive a weekly phone call from a helper to see how they are doing and to check on their progress.

Step 2: Problem Management Plus (PM+)

PM+ is a new, brief, psychological intervention program based on cognitive behavioral therapy (CBT) techniques that are empirically supported and formally recommended by the WHO (Dua et al., 2011). The manual involves the following empirically supported elements: problem solving plus stress management, behavioral activation, facing fears, and accessing social support. Figure 2 shows a brief outline of the five sessions. In these 60-minute sessions participants may talk to trained non-professional helpers (who are supervised by registered (clinical) psychologists). We will follow this outline, except that we excluded all assessment instruments from the manual, since they are administered at the assessments instead of at the intervention sessions. PM+ has four core features: it is brief (five sessions); delivered by para-professionals; transdiagnostic thereby addressing depression, anxiety, PTSD, stress and problems as defined by people themselves; originally designed for people in low-income country communities but easily adaptable to different (vulnerable) populations, cultures and languages.

In this study, the delivery mode of the PM+ intervention will be flexible, with remote delivery in phases of the pandemic when physical distancing rules apply. The PM+ intervention has been culturally and contextually adapted. This is a future-oriented attempt towards a more holistic mental health care system that can flexibly switch between modes of delivery (e.g. remotely (e.g. Zoom) or face-to-face), depending on the needs and the specific containment measures

that apply, and the specific preferences and needs of the participant.

Protocol adherence

Protocol adherence will be ensured by weekly supervisions provided by the PM+ trainers/supervisors as well as the fidelity checklist (Dawson et al., 2016). In addition to these, audio records of the sessions will be used for fidelity checks. The sessions will be audio recorded with professional equipment only if the participant gives consent to be recorded.

[figure not shown]

Figure 2. Outline of five PM+ sessions (figure from PM+ Manual, WHO, 2016). We will follow this outline, apart from the PSYCHLOPS assessment which is excluded.

Helpers in PFA, DWM and PM+ interventions

In general, helpers selected to provide support to users should have at least primary school level literacy as well as good knowledge and skills in providing psychosocial support. Delivering PFA, DWM or PM+ can be learned by both professionals and non-professionals who are in a position to help people impacted by (very) distressing events. Helpers should speak the same language as the participant (as well as being able to communicate in English). It is not necessary for helpers to have a psychosocial or mental health background in order to be able to offer these interventions. Necessary skills include foundational helping skills, such as effective community and rapport-building skills, and experience supporting people in distress. For DWM but particularly PM+ helpers, it is also recommended that helpers experience receiving support using the stress management guide (i.e., practice using the stress management guide as a user with a colleague acting as the helper). If support is provided remotely, it is preferable that helpers have experience with remote support and receive training in this approach (e.g., EQUIP REMOTE). Practice sessions (e.g., providing support to other helpers, practice supporting persons with impairments) can help identify issues that may arise prior to working with users and build helper capacity. Helpers need to sign a confidentiality agreement and need to show a

certificate of conduct. Helpers may deliver either PFA, DWM and/or PM+, if they are trained (and supervised) in each intervention delivered.

Training PFA helpers

Before providing PFA, helpers will receive training to enhance knowledge and gain better understanding of appropriate psychosocial responses and skills in providing support to individuals exposed to adversity (Sijbrandij et al., 2020). This half- or one-day training (WHO, 2013) will include explanations of the basic concepts and PFA principles, how to support (very) distressed people, and how not to cause further harm by using participatory learning (i.e. role-play).

Training DWM helpers

Similar to PFA-helpers, the role of the coach in DWM is to provide brief motivational support to the participants; not provide specialized mental health services. Helpers should be empathetic and motivated to do this. Before working as a helper, helpers will receive a short training by academics and/or mental health-care professionals. Helpers will be trained in providing support using the stress management guide (i.e., practice using the stress management in role-plays with other helpers) and practice to deliver support remotely (i.e. practice providing support in role-play settings). Helpers will receive a written manual as a guide for the brief support sessions.

Training PM+ helpers

PM+ helpers will receive eight days of training, followed by three practice cases, on-the-job training, and close supervision during the whole trial by the PM+ trainers/supervisors. Audio records of PM+ sessions will also be used for supervision. The training program comprises of education about common mental disorders, basic counseling skills, delivery of intervention strategies and self-care (Rahman et al., 2016a). The additional criteria for PM+ providers include having completed a high-school education and complete the EQUIP 'Delivering Remote Services' training.

Trainers/supervisors

All DWM/PM+ helpers will be actively trained and supervised by registered (clinical) psychologists and will be continued to be monitored throughout the process. These clinicians will also independently assess and monitor treatment sessions at-random in order to ensure treatment adherence and fidelity. Furthermore, these expert clinicians will supervise the entire assessment and therapeutic process to reduce the burden on and risks for participants.

DWM/PM+ trainers/supervisors will be approximately five licensed mental health care professionals such as health-care psychologists or psychiatrists. They will be trained by a Master Trainer via a training-of-trainers (TOT) program, consisting of the same elements as the training for helpers, but also of training and supervision skills (Rahman et al., 2016a). The PM+ trainers/supervisors will be responsible for close supervision of the PM+ helpers. Therefore, as a next step, they will train DWM/PM+ helpers. Figure 3 shows how the TOT of PM+ is planned. Such training with continued supervision by professionals has been successfully used for (lay-)counselors before (Murray et al., 2011).

The research team at UNIVERSITY OF VERONA will be responsible for arranging the trainings and supervision for the lay helpers. Supervision of the helpers by the trainers/supervisors will take place on a weekly basis (Dawson et al., 2016). This will be done remotely or face-to-face, depending on the preference of the trainers/supervisors and accounting for COVID-19 regulations. The trainers/supervisors will also receive supervision by the Master trainer when necessary.

[figure not shown]

Figure 3. Training of Trainers/Supervisors and DWM/PM+ Helpers

7.2. USE OF CO-INTERVENTION (IF APPLICABLE)

Not applicable

7.3. ESCAPE MEDICATION (IF APPLICABLE)

Not applicable

8. METHODS

8.1. STUDY PARAMETERS/ENDPOINTS

All participants will have five assessments (T0-T4), mostly by filling out online questionnaires. The five assessments take place at the following time-points (see also Figure 1):

T0: Screening for eligibility including psychological distress

T1: Baseline assessment

T2: 2 weeks post DWM intervention assessment

T3: 1-week post PM+ intervention assessment

T4: 2-months post PM+ intervention assessment

8.1.1. Main study parameter/endpoint

The primary endpoint will be the decrease in symptoms of depression and anxiety from baseline to two-month follow-up after the PM+ intervention ended, measured through the combined sum score of the Patient Health Questionnaire-9 (PHQ-9) and Generalized Anxiety Disorder (GAD-7) previously validated as the PHQ-ADS (Kroenke et al., 2016; 2019). A description of the measure(s) can be found under 'Study Procedures'. Based on prior studies on PM+ in Pakistan and Kenya (Rahman et al., 2016b; Bryant et al., 2017) where PM+ was administered as a standard treatment, we expect to detect a Cohen's *d* effect size of 0.3 in the PM+ group at 2 months post-treatment.

8.1.2. Secondary study parameters/endpoints (if applicable)

1. Level of depression (PHQ-9)
2. Level of anxiety (GAD-7)
3. Severity of posttraumatic stress disorder (PCL-5)
4. Resilience based on exposure to stressful (general- and COVID-19 related-) events (MIMIS)
5. Quality of life (EQ-5D-5L)
6. Cost of care: impact on use of health system, other services, time out of employment and other usual activities and need for informal care (CSRI schedule)

The measurement instruments are described under 'Study procedures'.

8.1.3. Other study parameters

The measurement instruments are described under 'Study procedures'.

1. Demographic data
2. Exposure to adverse life-events (BTQ)
3. Treatment fidelity (DWM: tracking app usage based on meta-data, PM+: audio records, checklists)
4. Level of self-identified complaints during PM+ ("Psychological Outcomes Profiles" (PSYCHLOPS))
5. Satisfaction (qualitative assessment in study phase 3)

6. Acceptability of the program (qualitative assessment in study phase 3)
7. Implementation indicators: reach, dose, resource use, costs of recruiting, training and retaining staff delivering the stepped-care program, program costs, adaptation, the process, quality.

8.2. RANDOMIZATION, BLINDING AND TREATMENT ALLOCATION

After the screening and the baseline assessment, participants will be randomized to either the treatment group (n=105) or the comparison group (n=105), with an equal probability of assignment to each group (allocation ratio 1:1). The trial is a single-blind RCT (i.e. outcome assessors are blind to treatment allocation). Randomization will be carried out through computerized software (e.g. Castor) using limited block size (e.g. 6-12 participants per block) and will be performed by an independent person who is not involved in the assessment of participants. If participants are randomized into the treatment group, they will be allocated to a DWM helper. This is also done blind by an independent person who is not involved in the assessment. The allocated helper will send an e-mail to the participant to set up a time and date for a first acquaintance telephone call before the intervention starts. During this call, the weekly support calls of the DWM helper will be discussed and planned. If participants still meet the inclusion criteria 2 weeks after the DWM program ended, they will be contacted by the PM+ helper (might be the same helper as for DWM) to plan five consecutive (tele-conferencing) meetings of 60 minutes with the participant. The first session will be scheduled within a few days and not longer than one week after the pre-intervention assessment.

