5. STUDY DESIGN

The study consists of a single-blind randomized controlled trial (RCT), that will include a qualitative analysis in its final phase. As a preliminary work, we conducted a qualitative study to assess the needs of ARM resettled in Italy and to inform the adaptation of the DWM/PM+ interventions. The preliminary phase has been completed and was described in a separate protocol for which ethical approval was granted by the Comitato di Approvazione della Ricerca sulla Persona – CARP – of the University of Verona.

Randomized controlled trial (stepped-care DWM/PM+ intervention with Psychological First Aid and care-as-usual vs. Psychological First Aid and care-as-usual alone).

The final phase of the RCT will include a process evaluation with qualitative interviews and focus groups to assess barriers and facilitators of engagement and adherence to the stepped-care intervention and opportunities for scaling up the implementation of the intervention.

Box 2. Summary of the present research.

Randomized controlled trial: the DWM/PM+ programs will be evaluated in a RCT. Participants will be screened for elevated distress (K10; see Figure 1). We will conduct a RCT in ARM with increased psychological distress to determine whether the stepped care intervention (i.e. DWM/PM+) leads to stronger decreases in mental health outcomes, and increase in wellbeing among compared to care-as-usual (CAU). This phase is designed as a randomized, single-blind parallel-group trial with one treatment group (n=105) and one comparison group (n=105). All participants in both the treatment and the comparison group will receive Psychological First Aid (PFA) and CAU. In addition to PFA and CAU, participants randomized into the treatment group will receive the DWM/PM+ stepped-care intervention, while participants randomized in the comparison group will receive PFA and CAU only.

All participants in the treatment group (i.e. those who receive DWM and PM+ and those who only receive DWM because symptoms subside) will be followed for a period of 2 months after the end of the PM+ session (see Figure 1 for assessment points).

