6.4. SAMPLE SIZE CALCULATION

A total number of 212 participants will be included. Based on prior studies on a PM+ intervention (Bryant et al., 2017; Rahman et al., 2016b), we aim to detect a small to medium effect size Delta (defined as the square root of the ratio of the variance of the tested effect to the comparison error variance) of 0.3 in the PM+ group at 2 months post-treatment based on the primary composite outcome PHQ-ADS (Kroenke et al., 2016; 2019). The PHQ-ADS is the combined sum score of depression and anxiety symptoms of the PHQ-9 and GAD-7, respectively and has shown good internal consistency ($\alpha = .88$ to $.92$) (Kroenke et al., 2016; 2019). A power calculation for an ANOVA repeated

measurement design with two time-periods to identify the effect of treatment at the last endpoint suggests a minimum sample size of $N=74$ per group (power=0.95, $\alpha=0.05$, two-sided, $\rho=0.9$). Taking into account 30% attrition, we aim to include a total number of 212 participants (106 in the stepped-care DWM/PM+ treatment group - with PFA and CAU - and 106 in the PFA and CAU comparison group).

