10.1 PRIMARY OUTCOME(S)

The statistical analysis of the RCT will estimate effectiveness of the stepped-care DWM/PM+ with PFA and CAU intervention compared to PFA and enhanced CAU alone, with PHQ-ADS score as the primary study outcome.

The primary outcome will be summarized using number of subjects (n), minimum and maximum; and means, standard deviations (SD) for normally distributed data, or medians and inter-quartile ranges for non-normally distributed data. To measure comparisons at baseline between the two treatment groups t -tests (continuous variables) or chi-squared test (categorical variables) will be conducted for normally distributed data; Mann-Whitney tests will be conducted for continuous non-normally distributed data.

Both intention-to-treat (ITT) analysis, including all randomized participants ($n=212$), and completers' (per protocol - PP) analysis will be carried out. The main conclusion of the trial will be based on the ITT analysis of the primary outcome. A secondary analysis of the primary outcome will also be presented using the PP population.

The statistical analysis will be masked, i.e. the trial statistician will be blinded to the treatment groups until the analysis has been completed. Moreover, the trial statistician will not be involved in determining participants' eligibility, in administering the intervention, in measuring the outcomes or in entering data.

To estimate the treatment effect, a linear mixed model will be employed for the primary endpoint analysis, which will have treatment as fixed effects, baseline measurement of primary endpoint as covariate, and subject as random effects. The mean difference between two treatment arms at each visit/time together with its 95% confidence interval will be derived from the mixed model. Covariate-adjusted mixed model of primary endpoint will also be performed by adding pre-specified covariates at baseline (gender, age, education, prior trauma, COVID-19 related events and stressor list) into the above model.

Missing data

Missing data will be treated as missing at random (MAR). No imputations of missing values will be made, as multilevel models can deal with missing data (Singer, Willett & Willett, 2003).

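### Section 8.2 and Box 2 plan 105 per arm (210 in total), against 106 per arm (212) in section 6.4; the protocol's own calculation gives 106

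*Protocol*

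**What the plan says.** The protocol gives two sizes for the same trial.

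**210 in total**
- Section 8.2 (randomisation): "participants will be randomized to either the treatment group (n=105) or the comparison group (n=105", with 1:1 allocation.
- Section 5, Box 2: "one treatment group (n=105) and one comparison group (n=105".

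**212 in total**
- Section 6.4 (sample size): "A total number of 212 participants will be included". It splits them as "106 in the stepped-care DWM/PM+ treatment group" and "106 in the PFA and CAU comparison group".
- Section 2 (summary): n=212 for the study population.
- Section 10.1 (ITT analysis): "including all randomized participants ($n=212".

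The per-arm figure of 106 appears only in section 6.4. The summary and section 10.1 give the total alone. Section 6.4 derives its figure from a minimum of 74 per group and an allowance of 30% attrition. Section 8.5 says that withdrawn participants are not replaced and relies on the same 30%.

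**The concern.** All five statements are current text, and nothing marks either number as approximate. The planned sample size tells the team when recruitment is complete, and it is the figure against which actual enrolment will later be judged. Section 8.2 is a natural place to look when the allocation list is set up. A team that took its target from there would stop at 210, and section 10.1 would then describe a set of 212 that was never randomised. A later reader could not tell whether 210 was full recruitment or a shortfall of two.

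**Working it through.** **Inputs, all from section 6.4 unless noted.** Delta = 0.3, defined there as the square root of the variance of the tested effect over the comparison error variance; power 0.95; two-sided alpha 0.05; minimum 74 per group; attrition 30%. Per-arm figures: 106 (section 6.4) and 105 (section 8.2 and Box 2).

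**1. Reproduce the 74.** Use a noncentral F test with 1 and N − 2 degrees of freedom and noncentrality N × Delta², where N is the total over both groups.
- 73 per group: N = 146, 146 × 0.09 = 13.14, power 0.9496.
- 74 per group: N = 148, 148 × 0.09 = 13.32, power 0.9521.

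So 74 is the smallest group size that reaches 0.95, as the protocol states.

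**2. Reproduce the 106.** 74 / (1 − 0.30) = 105.71, rounded up to 106 per arm; 2 × 106 = 212. Section 6.4 is reproduced exactly.

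**3. Expected completers under each figure.**

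| Randomised per arm | Total | Completers per arm at 30% attrition | Completers in total | Against 74 per arm |
|---|---|---|---|---|
| 106 | 212 | 106 × 0.70 = 74.2 | 148.4 | met |
| 105 | 210 | 105 × 0.70 = 73.5 | 147 | 0.5 short |

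For 105 to leave 74, attrition could be at most 1 − 74/105 = 29.5%.

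**4. Power at the expected number.** With 147 completers (73 in one arm and 74 in the other), the noncentrality is 147 × 0.09 = 13.23 and power is 0.9508. This is above 0.95 and 0.0013 below the 0.9521 at 148.

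**5. Does the size depend on how the 0.3 is read?** Section 8.1.1 and the summary call it Cohen's d, so the step from 73.5 to 74 per arm was repeated with d = 0.3 and a correlation of 0.9.
- Baseline-adjusted analysis: 0.9865 to 0.9870.
- Change score: 0.9824 to 0.9830.
- Final score only: 0.4438 to 0.4463.

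The step never moves power by more than 0.25 percentage points. None of these readings gives 74 as the required size (they give 55, 58 and 289), so the Delta definition in section 6.4 is the one to use for this check.

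**The case against.** The best defence is that the difference has no practical effect. Section 6.4 states the total outright and justifies it, and two other sections repeat that total. The 105s are figures in parentheses, and section 8.2 states no rule for stopping recruitment. The shortfall is half an expected participant per arm on a round attrition assumption. The primary analysis is also a mixed model over all randomised participants, so someone without the last visit but with an earlier follow-up still contributes. All of this stands, and it limits the size of the point. It does not remove the contradiction.

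A reader might infer more, in three ways that the documents do not support.
- **That 105 per arm misses the stated power of 0.95.** This needs both arms rounded down to 73, or 146 completers (power 0.9496). The expected number is 147, at which 0.95 is met.
- **That the ITT set changes or is misdefined.** Section 10.1 defines it by rule, as everyone randomised. The set follows actual enrolment, and only the printed 212 would be wrong.
- **That section 10.1 also states 106 per arm.** It gives only the total.

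It could also be said that 210 suits blocked randomisation: it divides into whole blocks of 6 or 10, within the example range of 6 to 12 in section 8.2, and 212 does not. The protocol does not give this reason, and a list need not end on a complete block.

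**Conclusion.** The point holds as a consistency error. Box 2 and section 8.2 state 105 per arm, and section 6.4, the summary and section 10.1 state or imply 106. Only 106 follows from the protocol's own 74 per group and 30% attrition. That 105 arose by cutting 105.71 down instead of rounding it up is plausible, but it is an inference.

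The size is small: two participants in the planned total, half an expected completer per arm, and about 0.1 percentage points of power, with 0.95 still met. The power figures rest on the Delta definition in section 6.4 and on attrition of exactly 30% in each arm. The contradiction rests on neither. No analysis or estimate changes.

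**What to change.** In Box 2 (section 5) and in section 8.2, change n=105 to n=106 for each group. Section 6.4, the summary and section 10.1 can stay as they are, and every section then states or implies 212. Check that the allocation list allows for at least 212; if it was prepared for 210, extend it.

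The cost is a change of wording in two places, submitted to the Ethics Committee under section 12.3 if a favourable opinion has already been given. It adds two participants relative to section 8.2 and none relative to section 6.4.
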